### **5.2.2. Exclusion Criteria**

Patients will not be enrolled if they meet any of the following exclusion criteria:

IIH related exclusion criteria:

1. Presence of venous sinus thrombosis on brain imaging by either magnetic resonance or computerised tomographic venography
2. Previous IIH surgery including CSF shunt, optic nerve sheath fenestration or dural venous sinus stent or sub-temporal decompression
3. Previous bariatric surgery within the last 3 months or intention during the trial
4. Abnormal neurological examination (aside from papilloedema and consequent visual loss or sixth or seventh nerve palsy or palsies)
5. Treatment to lower ICP within 1 week prior to screening visit (e.g., acetazolamide, topiramate (including if used as a migraine preventative),

Study Number: INVEX-CLIN-IIH-301	Compound No.: Presendin
Protocol	Version: 3.0

diuretics, glucocorticoids (I.V., injectable steroids or oral (including dexamethasone and prednisolone)). (Nasal, inhaled, or topical steroids are allowed)

6. Use of any drugs known to cause intracranial hypertension, including exposure to fluoroquinolones, lithium, vitamin A, or tetracyclines within 2 months prior to diagnostic LP

Vision related exclusion criteria:

7. Any disease other than refractive error that causes visual loss in the study eyes. Where there is uncertainty this would be determined by the Independent Adjudication Committee [IAC]
8. Refractive error worse than +/- 6.00 sphere or worse than +/- 3.00 cylinder in study eyes. In addition, participants with myopia of worse than -6.00 D sphere but less than or equal to -8.00 D sphere are eligible if the subject wears a contact lens for all perimetry examinations with the appropriate correction
9. Inability to perform a reliable visual field examination as deemed by the Visual Field Reading Centre in the study eyes. Where there is uncertainty this would be evaluated by the Independent Adjudication Committee [IAC]

Headache related exclusion criteria:

10. Does not complete  $\geq 6$  days of electronic/paper trial diary during the 7-day screening period

Other exclusion criteria:

11. Untreated previously diagnosed obstructive sleep apnoea with historically recorded apnoea-hypopnea index greater than 15
12. Glucagon like peptide-1 receptor agonist within last 4 weeks prior to screening
13. COVID-19 vaccine within 2 weeks prior to screening
14. Allergy/known hypersensitivity to the active substance and/or excipients of the investigational product
15. Has known contraindications to glucagon like peptide-1 (GLP-1) receptor agonists (e.g., ketoacidosis, severe gastrointestinal disease, pancreatitis, renal impairment) which may affect the safety of the patient
16. Using any glucose-lowering medication
17. Currently taking warfarin

Study Number: INVEX-CLIN-IIH-301 Protocol	Compound No.: Presendin
	Version: 3.0

18. Alanine transaminase (ALT) or aspartate transaminase (AST)  $\geq 2x$  the upper limit of normal (ULN), total bilirubin  $\geq 1.5x$  ULN, or alkaline phosphatase (ALP)  $\geq 1.5$  ULN at screening (Note – patients with elevated total bilirubin are not excluded if they meet criteria for Gilbert’s syndrome, including: bilirubin is predominantly indirect [with normal direct bilirubin level]; and ALT, AST and ALP  $\leq 1x$  ULN)
19. Kidney disease (as defined by serum cystatin C-based estimated glomerular filtration rate [eGFR]  $< 55$  mL/min/1.73 m^2, calculated at investigator site)
20. Any of the following abnormalities in clinical laboratory tests at screening, as assessed by the central laboratory and confirmed by a single repeat, if deemed necessary: *Hemoglobin*  $< 10$  g/dL ( $< 100$  g/L); *Platelet count*  $< 75 \times 10^9/L$  ( $< 75,000/mm^3$ )
21. Using recreational or illicit drugs at the time of signing the informed consent, or recent history (within the last year) of drug or alcohol abuse or dependence according to the DSM-5 criteria, that in the opinion of the investigator puts the patient at risk
22. Is unable to self-administer the trial medication (or unable to administer trial medication with support) after receiving training during the Screening period
23. History of any clinically significant disease or disorder that, in the opinion of the investigator, may either put the patient at risk because of participation in the trial or influence the results or the patient’s ability to participate in the trial
24. Any contraindication to lumbar puncture procedure in the opinion of the investigator
25. Has participated in any other interventional trial within 1 month prior to the screening visit.
26. Is pregnant or breastfeeding

Note: Use of headache preventative medication is allowed at enrolment (except for Topiramate). Changes to headache preventative medication during the trial should be made in consultation with the IAC – see section [10.1.2](#)

Study Number: INVEX-CLIN-IIH-301	Compound No.: Presendin
Protocol	Version: 3.0

## 6. TRIAL ASSESSMENTS AND PROCEDURES

### 6.1. Procedures at Each Visit

Trial procedures and timings are presented in the Time and Events Table, [Table 1](#).

No procedures should be performed prior to obtaining informed consent. All visits (except telephone call visits) should be performed at the clinic. Should a clinic visit not be possible, due to a patient self-isolating, the visit will be conducted at the earliest opportunity and will not constitute a protocol deviation.

#### 6.1.1. Visit 1 Screening

The screening period must be a minimum of 7 days, up to a maximum of 10 days. Visit procedures can be performed in a single visit or over a number of visits during the screening period. Ideally all screening procedures should be performed on the same day.

- Obtain patient's written informed consent
- Eligibility criteria
  - Including confirmation that diagnostic LP occurred within the last 4 weeks with an opening pressure  $\geq 25$  cm CSF in lateral decubitus position
- Demographics (sex, age and ethnicity)
- Medical and ophthalmic history
- Concomitant medication history
- Headache history (including family history of migraine (a first degree relative with and migraine) and headache in the 7 days prior to diagnostic LP)
- Headache preventative medication review
- Headache diary dispensed and diary training – to be performed on first day of screening.
- Vital signs (triplicate readings for blood pressure and heart rate will be taken at 1-minute intervals)
- Height, body weight and BMI
- Full physical examination
- Urine pregnancy test (for women of childbearing potential)
- Electrocardiogram

Study Number: INVEX-CLIN-IIH-301 Protocol	Compound No.: Presendin
	Version: 3.0

- Visual Assessments to both eyes
  - Frisén grading will be initially assessed by the site and then the presence of papilloedema verified by the OCT Reading Centre. Where there is uncertainty, fundus photos and or ultrasound scan (B scan) of the optic nerve may be conducted for evaluation by the IAC to confirm eligibility.
  - Optical coherence tomography imaging
    - Sites should initially check the scan quality. The OCT scan should then go through the upload process to the OCT Reading Centre, without delay. The OCT scan will then be reviewed by the OCT Reading Centre for a full quality assessment. The report from the OCT Reading Centre will be sent to the site. Where the OCT is of insufficient quality it should be repeated as soon as possible at an unscheduled visit. Where the OCT processing is of insufficient quality it should be reprocessed as soon as possible by the site.
  - Humphrey Visual Field (24-2 SITA-Standard using a size III white stimulus)
    - Sites should initially check the performance quality of the HVF (to ensure no more than 15% false positives). The HVF should then be uploaded to the Visual Field Reading Centre without delay (an initial quality assessment takes place during the upload procedure). The HVF will then be reviewed by the Visual Field Reading Centre for a full quality assessment. The report from the Visual Field Reading Centre will be received by the site. Where the visual field is of insufficient quality it should be repeated at an unscheduled visit without delay, and where there is uncertainty about eligibility this should be referred to the IAC.
  - Visual Acuity (LogMAR score)
- Laboratory assessments
- Trial medication training. Patients will be asked to self-administer 1 dose of placebo at the screening visit to ensure they are comfortable with self-injection. Patients who are not comfortable will be excluded

### **6.1.2. Visit 2 Baseline**

- Review eligibility criteria
- Concomitant medications review
- Headache preventative medication review

Study Number: INVEX-CLIN-IIH-301 Protocol	Compound No.: Presendin
	Version: 3.0

- Review headache diary (Patient must meet required number of headache days as per inclusion criteria. If the headache diary exceeds 7 days, then eligibility will be based on the last 7 days of the screening period, i.e., the 7 days prior to randomisation visit)
- Vital signs (triplicate readings for blood pressure and heart rate will be taken at 1-minute intervals)
- Body weight and BMI
- Adverse events review
- Targeted physical examination
- Urine pregnancy test (for women of childbearing potential)
- Electrocardiogram
- Visual Assessments to both eyes
  - Frisén grading will be assessed by the site
  - Optical coherence tomography imaging
    - Sites should initially check the scan quality. The OCT scan should then go through the upload process to the OCT Reading Centre, without delay. The OCT scan will then be reviewed by the OCT Reading Centre for a full quality assessment. The report from the OCT Reading Centre will be sent to the site. Where the OCT is of insufficient quality it should be repeated as soon as possible at an unscheduled visit. Where the OCT processing is of insufficient quality it should be reprocessed as soon as possible by the site.
  - Humphrey Visual Field (24-2 SITA-Standard)
    - Sites should initially check the performance quality of the HVF (to ensure no more than 15% false positives). The HVF should then be uploaded to the Visual Field Reading Centre without delay (an initial quality assessment takes place during the upload procedure). The HVF will then be reviewed by the Visual Field Reading Centre for a full quality assessment. The report from the Visual Field Reading Centre will be received by the site. Where the visual field is of insufficient quality it should be repeated at an unscheduled visit without delay.
  - Visual Acuity (LogMAR score)
- Patient reported outcomes: VFQ-25 & 10-item supp, HIT-6, SF-36 and EQ-5D-5L in diary
- Health Utilisation Form
- Laboratory assessments

Study Number: INVEX-CLIN-IIH-301 Protocol	Compound No.: Presendin
	Version: 3.0

- Anti-Drug Antibodies (ADA) blood sampling
- Patient randomised
- Trial medication training
- Trial medication dispensed and first dose self-administered at clinic. Patients will then be instructed to administer subsequent doses once weekly.
- Pharmacokinetic sampling (post-dose)

### **6.1.3. Visit 3 Telephone call**

All patients will receive a telephone call at visit 3 to conduct headache preventative medication review, check for any AEs or changes in medication, procedures outside of protocol, health utilisation, to remind them to complete their diary and to answer any questions they may have on administration or storage of the trial medication.

### **6.1.4. Visits 4, 5, 6, 7, 8 and 9 Clinic visits**

- Concomitant medication review
- Headache preventative medication review
- Headache diary review
- Vital signs (triplicate readings for blood pressure and heart rate will be taken at 1-minute intervals)
- Body weight and BMI (not visit 4)
- Adverse event review
- Targeted physical examination (visit 6, 8 and 9 only)
- Urine pregnancy test for women of child-bearing potential
- Electrocardiogram
- Visual Assessments to both eyes
  - Optical coherence tomography Imaging
    - Sites should initially check the scan quality. The OCT scan should then go through the upload processes to the OCT Reading Centre, without delay. The OCT scan will then be reviewed by the OCT Reading Centre for a full quality assessment. The report from the OCT Reading Centre will be sent to the site. Where the OCT is of insufficient quality it should be repeated as soon as possible at an unscheduled visit. Where the OCT processing is of insufficient quality it should be reprocessed as soon as possible by the site.

Study Number: INVEX-CLIN-IIH-301 Protocol	Compound No.: Presendin
	Version: 3.0

- Humphrey Visual Field (24-2 SITA-Standard)
  - Sites should initially check the performance quality of the HVF (to ensure no more than 15% false positives). The HVF should then be uploaded to the Visual Field Reading Centre without delay (an initial quality assessment takes place during the upload procedure). The HVF will then be reviewed by the Visual Field Reading Centre for a full quality assessment. The report from the Visual Field Reading Centre will be received by the site. Where the visual field is of insufficient quality it should be repeated at an unscheduled visit without delay.
- Visual Acuity (LogMAR score)
- Patient reported outcomes: VFQ-25 & 10-item supp, HIT-6, SF-36 and EQ-5D-5L in diary (not visit 4)
- Health Utilisation Form
- Laboratory assessments
- Pharmacokinetic blood sampling
- Anti-Drug Antibodies blood sampling
- Trial medication dispensing (not Visit 4) and accountability - patients should be reminded by the trial site to self-administer the trial medication weekly and to return used and unused trial medication at clinic visits

### 6.1.5. Visit 10

In the 4 weeks prior to visit 10, patients must not have missed more than one dose of trial medication and must have self-administered their final dose within 7 days of visit 10. Patients will be reminded by the trial site to self-administer trial medication weekly, to continue this until the completion of visit 10 and to bring their trial medication with them at visit 10 for return.

Where more than one dose has been missed during the 4 weeks preceding visit 10, visit 10 should be delayed. Self-administration of trial medication should continue at 7-day intervals and then visit 10 rescheduled to ensure no more than one dose of the trial medication has been missed in the previous 4 weeks. Visit 10 should be delayed no more than 14 days.

- Concomitant medication review
- Headache preventative medication review
- Headache diary review

Study Number: INVEX-CLIN-IIH-301 Protocol	Compound No.: Presendin
	Version: 3.0

- Vital signs (triplicate readings for blood pressure and heart rate will be taken at 1-minute intervals)
- Body weight and BMI
- Adverse event review
- Targeted physical examination
- Urine pregnancy test for women of child-bearing potential
- Electrocardiogram
- Visual Assessments to both eyes
  - Optical coherence tomography Imaging
    - Sites should initially check the scan quality. The OCT scan should then go through the upload process to the OCT Reading Centre, without delay. The OCT scan will then be reviewed by the OCT Reading Centre for a full quality assessment. The report from the OCT Reading Centre will be sent to the site. Where the OCT is of insufficient quality it should be repeated as soon as possible at an unscheduled visit. Where the OCT processing is of insufficient quality it should be reprocessed as soon as possible by the site.
  - Humphrey Visual Field (24-2 SITA-Standard)
    - Sites should initially check the performance quality of the HVF (to ensure no more than 15% false positives). The HVF should then be uploaded to the Visual Field Reading Centre without delay (an initial quality assessment takes place during the upload procedure). The HVF will then be reviewed by the Visual Field Reading Centre for a full quality assessment. The report from the Visual Field Reading Centre will be received by the site. Where the visual field is of insufficient quality it should be repeated at an unscheduled visit without delay.
  - Visual Acuity (LogMAR score)
- Lumbar puncture (within 7 days of last dose of trial medication)
  - Lumbar puncture to be performed ideally after visual assessments
  - Performed in the lateral decubitus position according to LP SOP
  - In some cases the lumbar puncture might be conducted using imaging guidance according to the preference of the individual and site. This could be using x-rays, computer tomography or ultrasound guidance.

Study Number: INVEX-CLIN-IIH-301	Compound No.: Presendin
Protocol	Version: 3.0

- If the procedure is not successfully performed it should be re-booked and repeated as soon as possible and the patient should remain on trial medication with the last dose within 7 days of the LP.
- Patient reported outcomes: VFQ-25 & 10-item supp, HIT-6, SF-36 and EQ-5D-5L in diary
- Health Utilisation Form
- Patient global impression of change question
- Laboratory assessments
- Pharmacokinetic blood sampling
- Anti-drug antibodies blood sampling
- Trial medication accountability

Where it is not feasible to conduct all of visit 10 procedures on the same day, these could be split provided visual assessments are performed before the LP and the patient remains on trial medication with the last dose within 7 days of the LP.

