#### **6.1.6. Visit 11 Follow-Up**

This visit will be performed as a telephone call to conduct headache preventative medication review and check for any AEs or changes in medication. In the event of any abnormal safety assessments identified at the end of treatment, e.g., abnormal ECG, abnormal routine laboratory results or ongoing adverse events, this visit may be performed at the clinic to repeat or follow up safety assessments.

A urine pregnancy test (for women of childbearing potential) will be performed, this can be conducted at home if the visit is performed by telephone call.

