### 11.2. Patient Withdrawal

#### 11.2.1. Patient Withdrawal from Trial Treatment

A patient will be withdrawn from treatment for any of the following reasons:

Study Number: INVEX-CLIN-IIH-301 Protocol	Compound No.: Presendin
	Version: 3.0

- Withdrawal of consent to continue in the trial. The reason for this will be documented if provided
- The Investigator or Sponsor, for any reason, decides the patient should be withdrawn from the treatment
- Lack of compliance with the trial medication is classified as <75% or >125% of scheduled doses over the course of the trial, excluding supply issues
- Adverse events, which cannot be tolerated by the patient
- Pregnancy during the treatment period

Patients will be encouraged to continue in the trial to the end of the randomised treatment period even if they stop trial medication so that data can be collected for the Intention-To-Treat (ITT) population.

If a patient is withdrawn from treatment during the randomised treatment period, they will be encouraged to return for all trial visits up to visit 10. If a patient does not want to return then at a minimum they should be encouraged to attend for visit 11 procedures as a safety follow-up visit.

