**13.3.1.5. Primary Estimand (Hypothetical assuming no concurrent procedures, irrespective of adherence to treatment)**

The primary estimand is defined as the following for the primary endpoint:

- Treatment difference in ICP measurement between Presendin and placebo at Week 24 for all patients who are randomised and start treatment, regardless of adherence to randomised treatment, where patients did not have medications or procedures likely to materially affect ICP.

The primary estimand for the initial secondary endpoint will be handled similarly to the primary endpoint using the “Hypothetical” approach. The initial secondary endpoint is defined as:

- Treatment difference in PMD between Presendin and placebo over 24-weeks for all patients who are randomised and start treatment, regardless of adherence to randomised treatment, where patients did not have medications or procedures likely to materially affect PMD.

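### The dosing condition on Visit 10, the only post-baseline LP, conflicts with a primary estimand that applies regardless of adherence and with the plan to keep following patients off drug

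*Protocol*

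**What the plan says.** References are to protocol version 3.0. The same conditions stand in version 1.0. Only appendix pages of version 4.0 are shown.

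- **Estimand.** Section 13.3.1.5 defines the primary ICP comparison at week 24 for "all patients who are randomised and start treatment, regardless of adherence to randomised treatment", had no ICP-affecting medication or procedure been used. Section 13.3.1.6 keeps the version in which everyone adheres as the secondary estimand.
- **Condition on the visit.** Section 6.1.5 states: "In the 4 weeks prior to visit 10, patients must not have missed more than one dose of trial medication". The final dose must fall within 7 days of the visit, and the LP item repeats that limit. A re-booked LP, or one split from the other procedures, requires the patient to remain on trial medication. If the condition fails: "Where more than one dose has been missed during the 4 weeks preceding visit 10, visit 10 should be delayed", and then: "Visit 10 should be delayed no more than 14 days". Table 1 footnote 12 repeats this. So does Section 7, which allows a longer delay in a global crisis.
- **Patients who stop.** Section 4.2.2 has patients withdrawn for intolerance continue with trial visits. Section 11.2.1 encourages withdrawn patients to attend up to Visit 10 and gives ITT data collection as the purpose. Table 1 footnote 11 says up to Visit 11.
- **Reluctant patients.** Section 11.2.1 adds: "If a patient does not want to return then at a minimum they should be encouraged to attend for visit 11 procedures". Section 6.1.6 says of Visit 11: "This visit will be performed as a telephone call". Table 1 lists no LP, perimetry or OCT there.

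**The concern.** Visit 10 is the only occasion after baseline on which ICP is measured. A patient who has stopped Presendin belongs to the primary estimand and is asked to attend, yet does not satisfy the condition for the visit. The protocol does not tell the site what to do. A site that follows 6.1.5 to the letter defers the visit and then has no instruction. A site that follows 11.2.1 takes the LP off drug.

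If the literal reading prevails, week-24 ICP is selected on recent adherence, which is a post-randomisation variable. The contrast then answers the secondary question under the primary label. Adherence could differ by arm: Section 1.2 lists nausea, vomiting and diarrhoea among the common exenatide reactions. Against that, Section 1.1.3 reports no withdrawals for adverse events in the small Phase 2 trial. Section 13.2.1.1 already allows for up to 50% missing final LPs and attributes refusals to the experience of the diagnostic LP. Loss driven by adherence is a different mechanism and is not considered there. An off-drug pressure that was not measured at week 24 cannot be recovered later.

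**Working it through.** **1. The plan's own figure.** Inputs from 13.2.1.1: difference 5 cm CSF; week-24 SD 9.4 (placebo) and 10.4 (Presendin); 60 or 72 final LPs per arm; 5% level, taken as two-sided because the alternative in 13.1 is that outcomes differ. The baseline to week-24 correlation ρ is not stated.

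σ = √((9.4² + 10.4²)/2) × √(1 − ρ²), and power = Φ(5 / (σ√(2/n)) − 1.96).

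With ρ = 0.4, σ = 9.91 × 0.917 = 9.09.

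- n = 60: 5/1.66 = 3.01, power 85.4% (stated: about 85%).
- n = 72: 5/1.51 = 3.30, power 91.0% (stated: 91%).

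Over ρ from 0 to 0.6 the range is 78.9–93.2% at 60 per arm and 85.7–96.6% at 72. The stated power is coherent at ρ of about 0.4 and is not at fault.

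**2. Who can meet the dosing condition.** List the 16 taken/missed patterns of the last four weekly doses before Day 169. Roll the four-week window forward 0, 7 and 14 days with every later dose taken.

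- 5 patterns have at most one missed dose and meet the count at once.
- 11 have more than one. Of these, 3 qualify after 7 days and 4 after 14 days.
- 4 never qualify within 14 days. All end missed–missed. At Day 183 the window reads missed, missed, taken, taken, which is two missed doses against a limit of one.
- A patient who never resumes has four of four missed and a last dose more than 7 days old, so fails both parts at any delay.

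This counts patterns, not patients. It gives no proportion of the trial.

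**3. What literal application would do to the estimate.** Let f be the share of Presendin patients off drug at week 24 and k the fraction of the 5 cm effect they retain. The protocol gives neither, so both are assumptions.

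Effect regardless of adherence = 5 × (1 − f(1 − k)). If only adherent patients are measured and imputation carries their values over to the rest, the estimate stays at 5. The overstatement is then 5f(1 − k).

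| f | k = 0 | k = 0.5 |
|---|---|---|
| 10% | 0.50 cm | 0.25 cm |
| 20% | 1.00 cm | 0.50 cm |
| 30% | 1.50 cm | 0.75 cm |

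For scale, with k = 0 and ρ = 0.4, power to detect the true regardless-of-adherence difference with 60 (72) LPs per arm is:

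- 77.4% (84.4%) at 4.5 cm;
- 67.4% (75.2%) at 4.0 cm;
- 56.0% (63.7%) at 3.5 cm.

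**The case against.** Off-drug follow-up is planned first. Sections 4.2.2 and 11.2.1 and footnote 11 all ask patients who stop to keep attending. Section 6.1.5 delays the visit and never says that the LP is cancelled. The 14-day limit can even be read as the date by which the visit takes place whatever the dosing history. Missing-data methods are left to the SAP, which is not shown. Dose Rationale (9.2) describes a product that takes 7–8 weeks to reach steady state, so complete loss of effect after two missed doses is an extreme case.

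Most of this stands, and it limits the claim. A reader might infer that the primary estimand cannot be estimated at all. The documents do not support that, because LPs off drug can be collected if sites follow 11.2.1. A reader might also infer that a telephone call replaces the LP for everyone who stops. Visit 11 is the minimum only for those who do not want to return.

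The contradiction itself is not answered. Section 4.2.2 sends patients to visits as the protocol describes them, and Visit 10 as described carries the condition. Nor can imputation be assumed to repair the loss. The factors named in 13.3.6 are treatment arm, centre, baseline value and stratification variables; adherence is not among them.

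**Conclusion.** The passages contradict one another on whether and when the LP is done in patients off drug. Sections 6.1.5 and 7 and footnote 12 condition it on recent dosing without exemption, while 4.2.2, 11.2.1 and 13.3.1.5 require data from those same patients. Permanent stoppers, and patients who missed the last two weekly doses before Day 169, cannot meet the condition within 14 days. No outcome is defined for them.

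The harm depends on how sites act. If they apply the condition literally, the observed contrast moves toward the secondary estimand. The 0.25–1.5 cm overstatement on 5 cm is an illustration, not a forecast. It assumes 10–30% off drug, 0–50% of the effect retained, no LPs from those patients, and imputation that corrects nothing. Whether the wording persists in version 4.0 cannot be checked.

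**What to change.** Reconcile 6.1.5, footnote 12 and Section 7 with 4.2.2, 11.2.1 and 13.3.1.5:

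- State that collection of Visit 10 outcomes (LP, perimetry, OCT) does not depend on dosing history in patients who have stopped or cannot meet the dosing condition within the allowed delay. Make this subject to continued consent and no contraindication, such as pregnancy.
- Record the date of the last dose and the number of missed doses, for use in the secondary estimand.
- In 11.2.1 and footnote 11, settle the disagreement between Visit 10 and Visit 11. Make Visit 10 the minimum visit requested of patients who stop, with Visit 11 in addition.

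No dosing rule is proposed. The cost is an amendment of wording; the LP is already in the schedule. Some LPs will be taken off drug, so the observed effect may be smaller and power for it lower. That is what the stated primary estimand requires.
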